9.4. Deaths, Serious Adverse Events and other Significant Adverse Events

Individual data listings of deaths and Serious AEs ([Table 14](#)) will be provided. The listing will include: Subject ID, AE Description, Duration, Reason Reported as an SAE, Severity, Relationship to Treatment, Alternate Etiology if not Related, Outcome, MedDRA SOC, and MedDRA PT.

9.5. Pregnancies

A female subject who participates in the trial and becomes pregnant will be asked to inform study personnel of a pregnancy occurring 30 days after the final study visit. A male subject who participates in the trial and whose female partner becomes pregnant 90 days after the final study visit will be asked to inform study personnel of the pregnancy. For all reported pregnancies, subjects will be asked to provide pregnancy outcome upon delivery or pregnancy termination to the clinical trial unit.

An individual data listing of pregnancy reports will be provided in [Listing 21](#), [Listing 22](#), [Listing 23](#), [Listing 24](#), and [Listing 25](#) if a pregnancy occurs post dosing. A by-subject list of birth control methods can be found in [Listing 20](#).

9.6. Clinical Laboratory Evaluations

Toxicity grade criteria can be found in [Table 3](#) and [Table 4](#). Unscheduled or repeated follow-up tests for medical or safety reasons will be listed but excluded from tabular and graphical summaries.

Clinical labs will not be collected for Day -1 if collected ≤ 7 days of dosing. In all cases, the most recent result in the database prior to dosing will be used as baseline. Missing clinical laboratory results on Day 4 or ET will not be imputed. If multiple Day -1 results exist for a subject, the latest result prior to dosing will be regarded as the baseline value.

All clinical laboratory results (chemistry, hematology, and urinalysis) will be listed ([Listing 9](#), [Listing 10](#), and [Listing 11](#)). Other laboratory results (viral serology, pregnancy tests, and confirmation of menopause) will be listed separately ([Listing 12](#)). Toxicology results will be shown in [Listing 13](#) and Breathalyzer results will be shown in [Listing 14](#). Abnormal laboratory results will be listed in [Table 16](#), [Table 17](#), and [Table 18](#).

Chemistry laboratory results will be summarized by parameter and severity (including maximum severity post-baseline) regardless of relatedness ([Table 19](#), [Table 20](#), [Table 21](#), [Table 22](#), [Table 23](#), [Table 24](#), [Table 25](#), [Table 26](#), [Table 27](#), [Table 28](#), [Table 29](#), [Table 30](#) and [Table 31](#)) and additionally the frequency of *related* laboratory toxicities will be summarized by parameter and severity (including maximum severity post-baseline; [Table 32](#), [Table 33](#), [Table 34](#), [Table 35](#), [Table 36](#), [Table 37](#), [Table 38](#), [Table 39](#), [Table 40](#), [Table 41](#), [Table 42](#), [Table 43](#), and [Table 44](#)). Summary statistics will be reported by parameter and scheduled visit, including change from baseline ([Table 45](#), [Table 46](#), [Table 47](#), [Table 48](#), [Table 49](#), [Table 50](#), [Table 51](#), [Table 52](#), [Table 53](#), [Table 54](#), [Table 55](#), [Table 56](#), [Table 57](#), [Table 58](#), and [Table 59](#)). Individual line plots showing the laboratory result over time will be shown by chemistry parameter ([Figure 3](#), [Figure 4](#), [Figure 5](#), [Figure 6](#), [Figure 7](#), [Figure 8](#), [Figure 9](#), [Figure 10](#), [Figure 11](#), [Figure 12](#), [Figure 13](#), [Figure 14](#), [Figure 15](#), [Figure 16](#) and [Figure 17](#)). Subjects will not be labeled in the line plots, as the purpose of the figures is to give an overall trend of trajectory. The following chemistry parameters will be included in summaries of severity: sodium, potassium, bicarbonate, glucose, blood urea nitrogen, creatinine, protein, albumin, aspartate aminotransferase (AST), alanine aminotransferase (ALT), alkaline phosphatase, and bilirubin. The following chemistry parameters will be included in tables of summary statistics and in graphical plots: sodium, potassium, magnesium, chloride, bicarbonate, glucose, blood urea nitrogen, creatinine, protein, albumin, AST, ALT, alkaline phosphatase, bilirubin, and direct bilirubin.

Hematology laboratory results will be summarized by parameter and severity (including maximum severity post-baseline) regardless of relatedness ([Table 60](#), [Table 61](#), [Table 62](#), [Table 63](#), [Table 64](#), [Table 65](#), [Table 66](#), [Table 67](#) and [Table 68](#)) and additionally the frequency of *related* laboratory toxicities will be summarized by parameter and severity (including maximum severity post-baseline; [Table 69](#), [Table 70](#), [Table 71](#), [Table 72](#), [Table 73](#), [Table 74](#), [Table 75](#), [Table 76](#) and [Table 77](#)). Summary statistics will be reported by parameter and scheduled visit, including change from baseline ([Table 78](#), [Table 79](#), [Table 80](#), [Table 81](#), [Table 82](#), [Table 83](#), [Table 84](#), [Table 85](#), [Table 86](#), and [Table 87](#)). Individual line plots showing the laboratory result over time will be shown by hematology parameter ([Figure 18](#), [Figure 19](#), [Figure 20](#), [Figure 21](#), [Figure 22](#), [Figure 23](#), [Figure 24](#), [Figure 25](#), [Figure 26](#), and [Figure 27](#)). Subjects will not be labeled in the line plots, as the purpose of the figures is to give an overall trend of trajectory. The following hematology parameters will be included in summaries of severity: hemoglobin, leukocytes, neutrophils, lymphocytes, monocytes, eosinophils, basophils, and platelets. The following hematology parameters will be included in tables of summary statistics

and in graphical plots: hemoglobin, hematocrit, erythrocytes, leukocytes, neutrophils, lymphocytes, monocytes, eosinophils, basophils, and platelets.

Urinalysis laboratory results will be summarized by parameter (protein, glucose, and hemoglobin) and severity (including maximum severity post-baseline) regardless of relatedness (Table 88, Table 89, Table 90, and Table 91) and additionally the frequency of *related* laboratory toxicities will be summarized by parameter and severity (including maximum severity post-baseline; Table 92, Table 93, Table 94, and Table 95). Because urinalysis parameters are not continuous (except for microscopy follow-up parameters in the event of abnormal urine), no tables of summary statistics or line plots will be produced for urinalysis results. If performed, results of microscopy follow-up tests to abnormal urine dipstick tests will be included in listings of urinalysis results.

In tables of severity, maximum severity observed for the parameter after dosing will be summarized. Tables of maximum severity for “Any Parameter” will be included for chemistry, hematology, and urinalysis laboratory results. In these tables, the maximum severity across all laboratory results in the respective category is summarized by visit, and from maximum severity post baseline. Ordinarily, only the maximum severity event will be counted in the summary tables. For instance, if subject has a mild decrease and a moderate increase observed post-dose, they will be counted once as a moderate increase for maximum severity post-baseline. In the exceptional case that a subject has an increase and a decrease of equal maximum severity, they will be counted twice for maximum severity post baseline, once for an increase and once for a decrease.

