7.7 Unscheduled Visit (if needed)

A subject may return to the clinic for an unscheduled visit at any time. The following activities at a minimum should be performed:

- Update MH
- Obtain VS
- Perform symptom-directed PE (if applicable)
- Update ConMeds
- Perform AE and SAE assessments
- Obtain blood and/or urine for clinical laboratory tests (if applicable)
- Counsel male and female subjects on the avoidance of pregnancy

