9.2.1.3 Reporting Adverse Events

AEs will be captured on the appropriate subject's source document and eCRF. Information collected for AEs includes event description, time of onset, investigator assessment of severity, relationship to the study drug, date of resolution of the event, seriousness, and outcome.

All AEs will be documented from the time of drug dosing up to and including Final Visit. AEs will be followed to resolution or until considered stable in the clinical judgment of the study investigator. Evaluation of AEs may require unscheduled visits and clinical and laboratory investigations, according to the clinical judgment of the Site PI and study physicians.

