they deteriorate after study drug dosing. For abnormalities noted from the time of study drug dosing, any Grade 1 or higher laboratory abnormality listed on the toxicity table in [Appendix C](#) will be entered in the database as an AE. Safety laboratory results that are abnormal according to the local laboratory reference range, but not considered a Grade 1 abnormality, will be evaluated by the study site clinician and reported as Grade 1 abnormality if clinically significant. If not clinically significant, these will not be considered laboratory AEs and will thus not be graded, but will be recorded in the source document and followed-up clinically at the discretion of the study site clinician. Abnormal laboratory values, performed as part of the complete CBC, clinical chemistry or UA but not listed in this toxicity table will be evaluated by the study clinicians, recorded in the source document and, if clinically significant, considered AEs and graded according to the criteria in [Section 9.2.1](#).

Protocol-specific laboratory normal range values in effect at the time of protocol submission are included in [Appendix B](#). Changes in these ranges during the trial will be handled as administrative protocol amendments and toxicity grades will be calculated using the new ranges from the effective date of the change. A regular protocol amendment will be submitted for these changes if a revised laboratory normal range value meets criteria for Grade 2 toxicity.

Gross blood in urine that is confirmed due to a menstrual cycle is not an AE (but is for all other reasons).

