3.2. Endpoints

Primary Endpoints:

- C_{max} , T_{max} , area under the curve (AUC) until last measurable concentration ($AUC_{(0-last)}$), and other PK parameters for zoliflodacin determined using plasma concentrations of zoliflodacin in blood samples collected on Day 1 [baseline (30 min before dosing) and 0.5 h, 1 h, 2 h, 3 h, 4 h, 6 h, 8 h, and 12 h after dosing], Day 2 [24 h and 36 h after dosing], Day 3 [48 h after dosing], and Day 4 [72 h after dosing], or early termination (ET), and measured using a validated high performance liquid chromatography tandem mass spectrometry (HPLC-MS/MS) method

Secondary Endpoints:

- The occurrence of treatment-emergent serious adverse events (SAEs) from administration of zoliflodacin on Day 1 to Final Visit (Day 8 ± 2), or ET
- The occurrence of unsolicited treatment-emergent adverse events (AEs) from administration of zoliflodacin on Day 1 to Final Visit (Day 8 ± 2), or ET
- The changes from baseline (up to 60 min before dosing) in vital signs (VS) following administration of zoliflodacin, as measured on Day 1 [1 h, 2 h, and 4 h after dosing], Days 2, 3, and 4 [24 h, 48 h, and 72 h, respectively, after dosing], and Final Visit (Day 8 ± 2), or ET
- The changes from baseline (Day -1) in clinical laboratory values following administration of zoliflodacin, as measured on Day 4, or ET
- The changes from baseline (up to 60 min before dosing) in electrocardiograph (ECG) parameters following administration of zoliflodacin, as measured on Day 1 [1 h, 2 h, and 4 h after dosing] and Day 4 [72 h after dosing], or ET

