14.3.5 Displays of Laboratory Results

14.3.5.1 Chemistry Results

Table 19: Chemistry Laboratory Results by Severity and Time Point – Any Chemistry Parameter

		None		Mild/ Grade 1		Moderate/ Grade 2		Severe/ Grade 3		Missing	
Time Point	N	n	%	N	%	n	%	N	%	n	%
Baseline	x	x	x	X	X	x	x	X	x	x	X
Day 4	x	x	x	X	X	x	x	X	x	x	X
Max Severity Post Baseline	x	x	x	X	X	x	x	X	x	x	X

Note: The “Max Severity Post Baseline” rows indicate the maximum severity experienced by each subject at any time point post baseline, including unscheduled assessments. N=Number of subjects in the Safety Population.

Table 20: Chemistry Laboratory Results by Severity and Time Point – Sodium

Time Point	N	None		Mild/ Grade 1 (Low)		Mild/ Grade 1 (High)		Moderate/ Grade 2 (Low)		Moderate/ Grade 2 (High)		Severe/ Grade 3 (Low)		Severe/ Grade 3 (High)		Missing	
		n	%	n	%	N	%	n	%	n	%	n	%	N	%	n	%
Baseline	x	x	x	x	x	X	x	x	x	x	x	x	x	X	x	x	x
Day 4	x	x	x	x	x	X	x	x	x	x	x	x	x	x	x	x	x
Max Severity Post Baseline	x	x	x	x	x	X	x	x	x	x	x	x	x	x	x	x	x

Note: The “Max Severity Post Baseline” rows indicate the maximum severity experienced by each subject at any time point post baseline, including unscheduled assessments. N=Number of subjects in the Safety Population.

Table 21: Chemistry Laboratory Results by Severity and Time Point – Potassium

This table will repeat Table 20 for Potassium.

Table 22: Chemistry Laboratory Results by Severity and Time Point – Bicarbonate

This table will repeat Table 20 for Bicarbonate.

Table 23: Chemistry Laboratory Results by Severity and Time Point – Glucose

This table will repeat Table 20 for Glucose.

Table 24: Chemistry Laboratory Results by Severity and Time Point – Blood Urea Nitrogen

This table will repeat Table 19 for Blood Urea Nitrogen.

Table 25: Chemistry Laboratory Results by Severity and Time Point – Creatinine

This table will repeat Table 19 for Creatinine.

Table 26: Chemistry Laboratory Results by Severity and Time Point – Protein

This table will repeat Table 19 for Protein.

Table 27: Chemistry Laboratory Results by Severity and Time Point – Albumin

This table will repeat Table 19 for Albumin.

Table 28: Chemistry Laboratory Results by Severity and Time Point – Aspartate Aminotransferase

This table will repeat Table 19 for Aspartate Aminotransferase.

Table 29: Chemistry Laboratory Results by Severity and Time Point – Alanine Aminotransferase

This table will repeat Table 20 for Alanine Aminotransferase.

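### SAP 9.6 keeps unscheduled laboratory tests out of the tables, but the laboratory shell footnotes include them in the maximum-severity row

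*SAP*

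**What the plan says.** SAP 9.6 sets a rule for all laboratory tables and figures: "Unscheduled or repeated follow-up tests for medical or safety reasons will be listed but excluded from tabular and graphical summaries".

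The shells in SAP Appendix 1 set another for one row. Under Tables 19, 20, 32 and 33, the footnote says that the Max Severity Post Baseline "rows indicate the maximum severity experienced by each subject at any time point post baseline, including unscheduled assessments". Every other chemistry, hematology and urinalysis severity table is defined as a repeat of one of these four shells, so it takes the footnote with it.

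The text of 9.6 also asks for this row. For chemistry: "Chemistry laboratory results will be summarized by parameter and severity (including maximum severity post-baseline) regardless of relatedness", with matching sentences for hematology and urinalysis. Further on, it says that in the severity tables "maximum severity observed for the parameter after dosing will be summarized". Neither sentence separates scheduled from unscheduled tests.

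The laboratory endpoint in SAP 3.2 is: "The changes from baseline (Day -1) in clinical laboratory values following administration of zoliflodacin, as measured on Day 4, or ET". Protocol 8.2.1.1 and Appendix A schedule the same single post-dose collection. Protocol 7.7 allows laboratory samples at an unscheduled visit, and Protocol 9.2.1.3 expects that some will be needed: "Evaluation of AEs may require unscheduled visits and clinical and laboratory investigations".

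**The concern.** Both rules are current SAP text, they apply to the same cells, and the plan does not rank them. A programmer who follows 9.6 computes the maximum over scheduled draws only. A programmer who follows the footnote adds the unscheduled results. Each can cite the SAP, and the counts can differ.

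An unscheduled test is most likely when something is being followed up, which is also when a worse grade may appear. Under the 9.6 sentence such a grade would be absent from the row labelled as the maximum, yet present elsewhere in the same report. The Safety Monitoring Committee is to advise on using the 4-g dose in a later QT study (Protocol 9.6.2), so the safety tables should not depend on a rule chosen after the grades are known.

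**Working it through.** The plan states no figure that depends on this rule, so there is nothing to reproduce. The check is a comparison of texts and a count.

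**1. Tables that carry the conflict** (SAP Appendix 1, last number minus first plus one):

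| Group | All results | Related only | Total |
|---|---|---|---|
| Chemistry | 19–31: 13 | 32–44: 13 | 26 |
| Hematology | 60–68: 9 | 69–77: 9 | 18 |
| Urinalysis | 88–91: 4 | 92–95: 4 | 8 |
| Sum | 26 | 26 | 52 |

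This is one row definition repeated 52 times, not 52 separate faults.

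**2. What the row contains under each rule.** Scheduled post-dose laboratory draws per completing subject: 1 (Day 4).
- SAP 9.6 sentence: the maximum over one draw is that draw, so the row essentially repeats the Day 4 row, apart from where an early-termination result is placed.
- Footnote: the maximum over Day 4 or early termination plus any unscheduled post-dose result, so the row can differ from Day 4.

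**3. Size for one subject.** Take a subject with no graded value on Day 4 and a Grade 1 value at an unscheduled test. The Grade 1 cell of the maximum row is 0/8 = 0% under the 9.6 sentence and 1/8 = 12.5% under the footnote. This takes the safety population as the eight planned subjects.

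**4. How many tables one such result changes.** If it is the subject's worst value for that analyte, it changes the analyte table (1). It also changes the Any Parameter table if it is the worst in its category (2). If it is judged related, the two related-only counterparts can change as well (up to 4).

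**5. How many subjects.** The documents give no rate of unscheduled laboratory tests, so this cannot be computed. It could be zero.

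**6. Where the result appears in any case.**
- Listings 9–11 hold all laboratory results, and Tables 16–18 list the abnormal ones (SAP 9.6).
- Protocol 9.2.4 has "any Grade 1 or higher laboratory abnormality listed on the toxicity table in" Appendix C entered as an adverse event when it is found after dosing, and SAP 9.3.2 puts laboratory adverse events into the adverse-event tables, figures and listings.

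**7. Urinalysis.** SAP Table 4, Note 4, lets microscopy supersede an abnormal dipstick. On that table's grades, dipstick blood of 2+ is Grade 2 and 6–10 red cells per field is Grade 1. A maximum taken over both gives Grade 2, although the result that supersedes is Grade 1. An inclusion rule for the row therefore has to cover this case.

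**The case against.** The strongest reply is that the footnote is simply the specific exception to a general rule. That is a reasonable guess at intent, but the SAP does not say so, and the 9.6 sentence names tabular summaries without qualification.

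A second reply is that the intent cannot be read from the rest of 9.6. This stands in part. The sentences asking for the maximum do not mention unscheduled tests. The near-redundancy of the row is only suggestive, because the same shells also serve vital signs, which have several post-dose time points; the row may be template text. Deleting the phrase about unscheduled assessments from the laboratory footnotes would also end the conflict. It would, however, keep a row that nearly duplicates Day 4 and can leave out a subject's worst grade.

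Third, the consequence is small. This stands. A reader might infer that a safety finding could vanish from the report. The documents do not support that: the listings and the adverse-event displays still carry it.

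A reader might also extend the point to the vital-sign and ECG tables, which use the same footnote. SAP 9.7 and 9.9 contain no exclusion sentence, so nothing conflicts there.

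Nor should a reader take comfort that the two rules agree whenever the Day 4 grade is the worst. In the 26 related-only tables, a Grade 2 unrelated result on Day 4 with a Grade 1 related result at an unscheduled test gives different rows. In the tables split by low and high, 9.6 counts a subject twice for an increase and a decrease of equal maximum grade, so an unscheduled result of equal grade in the other direction adds a count.

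**Conclusion.** The contradiction is real and confined to the laboratory severity tables. It is minor. It affects one row in each of 52 tables. One affected subject moves a cell by 12.5 percentage points at N = 8, and the number affected is unknown and may be zero. The tables are descriptive. The laboratory endpoint is change from baseline at Day 4 or early termination, which this row does not feed, and no other primary or secondary endpoint uses it.

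The preference for including unscheduled results rests on the purpose of a maximum-after-dosing row and on there being one scheduled post-dose draw. It does not rest on any statement of precedence in the SAP. A reader might go further and want repeated tests added to the row as well. The footnotes name only unscheduled assessments, and bringing in repeats would collide with the rule that microscopy supersedes an abnormal dipstick.

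**What to change.** Amend the sentence in SAP 9.6 before data lock, for example: *Follow-up tests that are unscheduled or repeated are listed, and are left out of by-visit rows, summary statistics and line plots; unscheduled post-dose assessments count toward the Max Severity Post Baseline rows, as the table footnotes state.*

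Keep the footnote wording as it stands and do not extend it to repeated tests. Add one line for urinalysis Tables 88–95: a dipstick result superseded by microscopy under Table 4, Note 4, does not count toward the maximum.

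The cost is one revised sentence and one added line, with no new data. The downside is that maximum grades may look slightly less favourable than under the present 9.6 wording.
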